6.2.2 Expansion Cohort

Prior to start of the expansion cohort, there will be a review of the dose modification plan for the expansion cohort by the PI and co-I's. Based on prior studies of chemotherapy-sparing front-line agents in FL (Morschhauser et al. 2018), we hypothesize a successful combination will demonstrate a complete response rate of greater than 50%, while an ineffective combination will demonstrate a complete response rate of less than 30%. Simon's two-stage design (Simon 1989) will be used to test the primary outcome of 6-month CR rate defined for each subject as a binary categorical variable using Lugano response criteria applied to the 6 month PET disease assessment. The null hypothesis that the true 6-month CR rate is 30% or lower will be tested against a one-sided alternative. In the first stage, 15 patients will be accrued. If there are 5 or fewer responses in these 15 patients, the study will be stopped. Otherwise, 17 additional patients will be accrued for a total of 32. The null hypothesis will be rejected if 13 or more responses are observed in 32 patients. This design yields a type I error rate of 0.10 and power of 0.80 when the true response rate is 50%. Patients treated at the MTD/RP2D in the Dose Finding Cohort will contribute towards the accrual goal for the Expansion Cohort.

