DURATION OF	CC-486: twelve 28-day cycles.	
ADMINISTRATION	Obinutuzumab: nine 28-day cycles. Obinutuzumab will start in cycle 1 in the dose finding arm and on cycle 4 of the expansion cohort.	
STATISTICAL METHODOLOGY	Dose finding: 3+3 design with 3 dose levels and 2 optional dose de-escalation levels.	

Expansion cohort: Simon 2-stage design with 80% power and a type I error rate (α) of 10% to detect a difference in the primary study outcome: $\geq 50\%$ 6-month complete metabolic response (CR) rate indicating an effective combination, versus $\leq 30\%$ 6-month CR rate indicating an ineffective combination.

LIST OF ABBREVIATIONS

ADCC Antibody-Dependent Cellular Cytotoxicity

AE Adverse Event

AESI Adverse Event of Special Interest

AML Acute Myeloid Leukemia

amu Atomic Mass Unit BMI Body Mass Index BSA Body Surface Area

BSD Biological Sciences Division CBC Complete Blood Count

CC-486 Investigational name for oral azacitidine (Celgene Corp.)

CCTO Cancer Clinical Trials Office

CD20 Cluster of Differentiation 20 (B-lymphocyte antigen)

CLL Chronic Lymphocytic Leukemia CR Complete metabolic Remission

CRF Case Report Form

CRA Clinical Research Associate

CRAC Clinical Research Advisory Committee
CTRC Clinical Trials Review Committee

DLT Dose Limiting Toxicity
DNA Deoxyribonucleic acid

DNMT Deoxyribonucleic acid methyltransferase

DOA Delegation of Authority

DSMB Data and Safety Monitoring Board

ECI Event of Clinical Interest

FDA United States Food and Drug Administration

FL Follicular Lymphoma

FLIPI Follicular Lymphoma International Prognostic Index

GELF Groupe d'Etude des Lymphomes Folliculaires

HBcAb Hepatitis B core Antigen HBsAg Hepatitis B surface Antigen

HBV Hepatitis B Virus
HCV Hepatitis C Virus
IB Investigators' Brochure
IDS Investigational Drug Services

IRB Institutional Review Board

IV Intravenous

JC Virus John Cunningham Virus MTD Maximal Tolerated Dose

NADPH Nicotinamide Adenine Dinucleotide Phosphate

NHL Non-Hodgkin Lymphoma
OCR Office of Clinical Research
ORR Overall Best Response Rate

OS Overall Survival
OTC Over the Counter
PD Progression of Disease
PFS Progression-Free Survival
PHI Protected Health Information

PI Principal Investigator

PML Progressive Multifocal Leukoencephalopathy

PO Per Os, Oral PR Partial Response

REDCap Research Electronic Data Capture software

RGU-CHO N-formylguanylribosylurea

RGU Guanlyribosylurea RNA Ribonucleic acid

RP2D Recommended Phase 2 Dose SADR Serious Adverse Drug Reaction

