2.5 METHOD FOR ASSIGNING SUBJECTS TO STUDY GROUPS

Subjects will be assigned to the dose-finding arm in cohorts of 3 patients until the RP2D is established (estimated 12-18 subjects). The next 15 enrolled subjects will be assigned to the expansion cohort, stage 1. The following 17 enrolled subjects will be assigned to the expansion

cohort, stage 2. Once the expansion cohort has reached a goal of 32 total patients, further enrollment will be closed. Patients will not be randomized and will be assigned to arms, cohorts and stages by the order of enrollment alone. No placebos will be used.

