2.7 PRIMARY STUDY ENDPOINTS

Dose-finding cohort:

- Recommended phase 2 dose, defined as the maximum tolerated dose up to dose level 3 (see Table 2)
- Rate of grade 3/4 adverse events
- Rate of discontinuation

Expansion cohort:

• Six-month complete metabolic response rate assessed by PET scan

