2.8 SECONDARY STUDY ENDPOINTS

- Overall survival both at the end of the trial and as a 5-year estimate
- Progression-free survival both at the end of the trial and as a 5-year estimate
- "CR30" complete metabolic response rate at 30 months post-treatment initiation
- Three-month CR rate after 3 cycles of treatment with venetoclax and CC-486 alone (expansion cohort only)

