3 SUBJECT SELECTION AND WITHDRAWAL

3.1 Number of Subjects

Twelve to eighteen subjects from any of the study sites are expected in the dose-finding arm, and 32 in the expansion cohort for a total of 44-50 patients.

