6.2 STATISTICAL METHODS

6.2.1 Dose Finding Cohort

A 3+3 trial design with 3 dose levels and 2 optional dose de-escalation levels will be used (see Section 4.2 for details). This rule-based design proceeds with cohorts of three patients; the first cohort is treated at a starting dose that is considered to be safe based on prior human studies, and the subsequent cohorts are treated at increasing dose levels that have been fixed in advance (Storer 1989). Safety and tolerability for the purpose of dose-finding for the three-drug combination will be assessed in the first 28-day cycle of therapy.

The definition of dose limiting toxicity (DLT) is as follows:

- Grade 3 or 4 treatment-related non-hematologic toxicity with the exceptions of fatigue, anorexia, nausea, and fever without neutropenia
- Grade 4 treatment-related hematologic toxicity (anemia, thrombocytopenia and/or neutropenia) either lasting > 7 days despite supportive care or complicated by hemorrhage
- Any grade 5 toxicity.

If none of the three patients in the first cohort experiences a DLT within a 28-day cycle, the dose level will be advanced to DL2. If one or more of the patients at a certain dose level experiences a dose-limiting toxicity, three more patients will be treated at the same dose level. If there are two or more DLTs in a cohort of 3-6 patients at dose level 1, three patients will be enrolled at DL-1. If there are two more DLTs at dose level -1, three patients will be enrolled at DL-2.

If the dose level has been advanced to level 2 already, and two or more patients in a cohort of 3-6 patients experience dose-limiting toxicity, the RP2D will be defined as dose level 1. If a dose level has been lowered to DL-1 or DL-2 and no patients experience a DLT, that dose will be the RP2D. If one patient in a cohort at DL-1 and DL-2 experiences a DLT, another three patients will be enrolled. If none of the subsequent cohort experience a DLT, the dose level will be taken as the RP2D.

If there are no DLTs at DL2, DL2 will be the RP2D.

NOTE: The RP2D will be determined based on an integrated evaluation of the efficacy, safety, and tolerability of all evaluated dosing cohorts.

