6.3 Subject Population(s) for Analysis

In the dose finding cohort, all enrolled patients who receive investigational agents will be subjected to study analysis. The all-treated population will be analyzed for the primary study outcomes of safety, tolerability and RP2D. In the expansion cohort, the intention-to-treat population of patients assigned to the treatment arm and who received at least one dose of an investigational agent will be used for analysis of the primary study outcome of CR rate as well as all secondary outcomes. The evaluable population will include patients who have completed 3 cycles of treatment and have a first interim response assessment data available, as well as patients with early progression and off-schedule disease assessment.

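### Section 6.2.2 counts dose-finding patients towards the 32 in the Simon test, sections 2.5 and 3.1 do not, and those patients start obinutuzumab three cycles earlier; the primary test set is undefined and the stated alpha of 0.0997 is not assured

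*Combined protocol and SAP*

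**What the plan says.** - **Section 6.2.2** sets the rule: stop if there are 5 or fewer CRs in 15 patients, otherwise add 17 and reject the 30% null with 13 or more CRs in 32. It then adds: "Patients treated at the MTD/RP2D in the Dose Finding Cohort will contribute towards the accrual goal for the Expansion Cohort".
- **Section 2.5**, once the recommended phase 2 dose (RP2D) is established: "The next 15 enrolled subjects will be assigned to the expansion cohort, stage 1". The 17 enrolled after them form stage 2, and order of enrolment alone decides the stage.
- **Section 3.1** expects 12-18 dose-finding patients and "32 in the expansion cohort for a total of 44-50 patients".
- **Section 6.3** bases the expansion cohort's primary CR analysis on "the intention-to-treat population of patients assigned to the treatment arm and who received at least one dose of an investigational agent". Carried-over patients are not mentioned.
- **Study Summary**, Duration of Administration: "Obinutuzumab will start in cycle 1 in the dose finding arm and on cycle 4 of the expansion cohort".
- **Section 6.1** reports alpha 0.0997, power 0.8038 and a 72.16% chance of stopping after 15 patients under the null.

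No section says how many dose-finding patients carry over or which stage they enter.

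**The concern.** Two statisticians following this plan could test different sets of 32 patients and reach different go/no-go decisions. Three consequences follow.

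First, the carried-over patients have a different treatment schedule at the time of the primary PET. Section 1.1.7 justifies the obinutuzumab-free window by the need to avoid confounding from an agent already known to work, so the protocol itself treats the timing of obinutuzumab as relevant to response. If CR differs by schedule, the stated error rates fail, in a direction that depends on which rate is higher.

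Second, even with equal CR rates, an unresolved contradiction lets the choice between 6.2.2 and 2.5 be made once the dose-finding responses are known.

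Third, carried-over patients have no obinutuzumab-free window. They cannot inform the three-month CR endpoint for venetoclax and CC-486 alone (section 2.8), which would rest on 26-29 patients instead of 32.

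**Working it through.** **Inputs.** Null 0.30, alternative 0.50, cut-offs 5/15 and 13/32 (6.1, 6.2.2). Number carried over: k = 3 or 6, the size of a 3+3 dose level (6.2.1). The CR rate q of carried-over patients is not in the documents, so it is varied. Entry to stage 1 is plausible by timing but is an assumption.

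**Schedules before the PET preceding cycle 7** (4.2.1.1, 4.2.1.2, 5.6.2). Dose finding: 3 infusions in cycle 1 + 5 in cycles 2-6 = 8, over 6 cycles. Expansion: 3 in cycle 4 + 2 in cycles 5-6 = 5, over 3 cycles.

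**Enrolment.** With no overlap, 12 + 32 = 44 and 18 + 32 = 50, as in 3.1. With overlap, 12 + 32 − 6 = 38 up to 18 + 32 − 3 = 47.

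**The plan's own figures.** With X1 ~ Bin(15, p) and X2 ~ Bin(17, p):

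- early stopping = P(X1 ≤ 5); at p = 0.30 this is 0.7216
- P(reject) = Σ over x = 6 to 15 of P(X1 = x) · P(X2 ≥ 13 − x); this is 0.0997 at p = 0.30 and 0.8038 at p = 0.50

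All three match 6.1, for one common CR rate.

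**Carry-over into stage 1.** The stage 1 count becomes Bin(k, q) + Bin(15 − k, p); stage 2 stays Bin(17, p). With expansion CR p = 0.30:

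| q | alpha, k = 3 | alpha, k = 6 |
|---|---|---|
| 0.20 | 0.0757 | 0.0557 |
| 0.30 | 0.0997 | 0.0997 |
| 0.35 | 0.1128 | 0.1268 |
| 0.42 | 0.1322 | 0.1704 |
| 0.50 | 0.1560 | 0.2277 |

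At q = 0.42, early stopping is 64.9% / 57.1% (k = 3 / 6) instead of 72.2%. The 42% is the CR rate in 1.1.4.2 for venetoclax plus obinutuzumab without CC-486. Section 1.2.3.2 gives 45% (95% CI 17%-77%) from the same cited source, so either direction is possible.

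**Carry-over into stage 2.** Stage 1 is Bin(15, p) and stage 2 is Bin(k, q) + Bin(17 − k, p). At q = 0.42, alpha is 0.1181 / 0.1370 and early stopping is unchanged.

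**Power, expansion CR 0.50, stage 1 entry.** 0.7706 / 0.7340 at q = 0.42; 0.8418 / 0.8744 at q = 0.60.

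**Choice after the data, every CR rate 0.30.** Pool only when that raises the chance of rejection: alpha = Σ over x of P(X = x) · max{P(reject | x carried-over CRs), 0.0997}, with X ~ Bin(k, 0.30). For k = 3, P(X = x) for x = 0 to 3 is 0.343, 0.441, 0.189, 0.027, and P(reject | x) is 0.0357, 0.0932, 0.1964, 0.3434. Hence 0.784 × 0.0997 + 0.189 × 0.1964 + 0.027 × 0.3434 = 0.1246. The same sum for k = 6 gives 0.1374.

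**Selecting the dose on response (worst case).** If the dose level with most CRs of L levels is carried into stage 1 and every CR rate is 0.30, alpha is 0.1340 / 0.1493 for L = 2 and 0.1559 / 0.1828 for L = 3 (k = 3 / 6).

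**Accrual-only reading.** If carried-over patients fill places but are not tested, and 15 expansion patients with the same cut-offs are kept in stage 1, the test has 29 or 26 patients. Alpha is 0.0566 / 0.0245 and power 0.7245 / 0.5657.

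**The case against.** The strongest reply is that 6.2.2 speaks of accrual and does not say these patients enter the test; 2.7 and 6.3 tie the primary CR endpoint to the expansion cohort. That reading is possible, but it does not save the plan: alpha falls and power drops well below the stated 0.80. Either reading of the sentence departs from the figures in 6.1 or leaves them unsupported.

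The inflation also depends on which null is meant. The table sets 30% for the expansion schedule. If the null is an average of 30% over the pooled 32, with carried-over CR at 42%, the expansion rate must be (0.30 × 32 − 0.42k) / (32 − k), or 0.2876 / 0.2723. Alpha is then 0.106 / 0.112 with stage 1 entry and 0.093 / 0.084 with stage 2 entry, close to nominal. This objection stands, because 6.2.2 does not name the schedule to which its null applies.

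It is also fair that nothing in the documents shows a 12-point CR gap caused by obinutuzumab timing. At 42% against 30% the expected pooled CR shifts only by k × 0.12 / 32, that is 1.1 / 2.3 percentage points.

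The post-hoc choice and dose-selection figures are upper bounds. A note in 6.2.1 does say: "The RP2D will be determined based on an integrated evaluation of the efficacy, safety, and tolerability of all evaluated dosing cohorts". But the operative rules there use toxicity in one 28-day cycle, and 2.7 defines the RP2D as the maximum tolerated dose up to dose level 3. Selection on response is a possibility, not an established fact.

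Finally, counting RP2D patients is a legitimate design choice if it is specified. Here it is not.

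**Conclusion.** The concern holds and must be fixed. The membership of the primary test set is contradictory between 6.2.2 on one side and 2.5 and 3.1 on the other, and 6.3 does not settle it. That conclusion rests on the text alone.

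The size of the effect on error rates is conditional. The stated alpha is not guaranteed, which is different from always being inflated. With expansion CR at 30% and 3-6 patients entering stage 1, alpha runs from 0.056 to 0.228 as their CR goes from 20% to 50%, and it equals 0.0997 if their CR is also 30% and the pooling decision and the dose did not depend on response. The post-hoc route to inflation, up to 0.125 / 0.137, needs no difference in CR between schedules.

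**What to change.** Delete the carry-over sentence in 6.2.2. Apply the 5/15 and 13/32 rule only to 32 patients assigned to and treated on the expansion schedule, as 2.5 and 3.1 already imply, and state in 6.3 that the primary CR population excludes dose-finding patients. Report six-month CR for the dose-finding patients at the RP2D separately; label any pooled estimate a sensitivity analysis. This restores the figures in 6.1.

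The cost is two sentences and the loss of a 3-6 patient saving in accrual. Planned enrolment does not rise.

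If the sponsor prefers to pool, the plan should fix how many patients count and in which stage before any dose-finding CR is known, restate alpha, power and early stopping over a range of CR rates for them, and bring 2.5, 3.1 and 6.3 into line. That costs no patients but needs recalculated operating characteristics and edits to three sections.

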6.3 Subject Population(s) for Analysis

In the dose finding cohort, all enrolled patients who receive investigational agents will be subjected to study analysis. The all-treated population will be analyzed for the primary study outcomes of safety, tolerability and RP2D. In the expansion cohort, the intention-to-treat population of patients assigned to the treatment arm and who received at least one dose of an investigational agent will be used for analysis of the primary study outcome of CR rate as well as all secondary outcomes. The evaluable population will include patients who have completed 3 cycles of treatment and have a first interim response assessment data available, as well as patients with early progression and off-schedule disease assessment.

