2 STUDY DESIGN

2.1 TYPE OF STUDY

The study will consist of two sequential single arms. Patients meeting enrollment criteria will be assigned non-randomly to the study arms based on order of enrollment. Neither patients nor investigators will be blinded to the assignment. First, a dose finding arm with a standard "3 + 3" design will use venetoclax, CC-486, and obinutuzumab combination therapy in three dose levels and two optional dose de-escalation levels to establish the RP2D and assess toxicity and tolerability of the triplet. Dose-limiting toxicity will be assessed during the 28 days of Cycle 1. If a safe and tolerable RP2D is established, the study will proceed with an expansion cohort using Simon two-stage and window designs. In the expansion cohort, the first three cycles will consist of a combination of venetoclax and CC-486 before obinutuzumab is added in cycle 4. Disease assessment will take place after cycle 3 and cycle 6 and will be graded according to the Lugano Criteria (B. D. Cheson et al. 2014). Adverse events (AEs) will be monitored throughout the trial, and graded in severity according to the guidelines outlined in the NCI Common Terminology Criteria for Adverse Events (CTCAE) version 5.0. This trial will be conducted in accordance with Good Clinical Practices.

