3.13 DATA COLLECTION AND FOLLOW-UP ON EARLY TREATMENT TERMINATION SUBJECTS

Subjects who are withdrawn from active treatment due to an AE or an SAE will remain enrolled in the trial for the purposes of tracking ongoing toxicity. Subjects will continue with the usual schedule of follow-up visits as feasible and will be included in the intention-to-treat analysis. Subjects who have voluntarily withdrawn from the active treatment will be asked to continue scheduled evaluations, complete an end-of-study evaluation, and be given appropriate care under medical supervision until the symptoms of any AE resolve or the subject's condition becomes stable.

Subjects who discontinue treatment for reasons other than disease progression will have post-treatment follow-up for disease status until disease progression, initiating a non-study cancer treatment, withdrawing consent, or becoming lost to follow-up. All subjects, including those who withdraw due to disease progression or complete the planned follow-up period, will be followed by telephone until death, withdrawal of consent, or the end of the study.

Subjects may be replaced in the trial as needed to ensure that the required number of evaluable subjects is achieved for the designated statistical analyses as put forth in Section 6.

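### RP2D is decided in the all-treated population with no DLT-evaluable set, so read literally a patient who leaves or is under-exposed in Cycle 1 without a DLT supports escalation

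*Combined protocol and SAP*

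**What the plan says.** Section 6.3 defines the dose-finding analysis set by treatment received: "all enrolled patients who receive investigational agents will be subjected to study analysis". It then assigns the RP2D to that set: "The all-treated population will be analyzed for the primary study outcomes of safety, tolerability and RP2D". No minimum number of doses or days of observation is attached.

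The DLT window is fixed in Section 2.1: "Dose-limiting toxicity will be assessed during the 28 days of Cycle 1". Section 6.2.1 applies it. The condition for moving up from the first level begins "If none of the three patients in the first cohort experiences a DLT within a 28-day cycle". After a DLT, "three more patients will be treated at the same dose level".

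The only definition of evaluable in Section 6 concerns response: "The evaluable population will include patients who have completed 3 cycles of treatment and have a first interim response assessment data available", with early progressors added. Section 3.13 allows replacement: "Subjects may be replaced in the trial as needed to ensure that the required number of evaluable subjects is achieved". It refers to Section 6 for what that number is.

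Three other provisions bear on the point:

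- Section 3.12 keeps patients taken off treatment for its listed reasons under monitoring.
- Section 8.2.1 follows adverse events for 30 days after the last dose.
- A note at the end of Section 6.2.1 says the RP2D will rest on an integrated look at efficacy, safety and tolerability across the dosing cohorts.

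**The concern.** A 3+3 decision uses the absence of DLTs among three patients as evidence that a level is tolerable. A patient who took a few doses and left, or who received much less than the assigned dose, supplies little of that evidence. Such a patient is nevertheless all-treated and has not had a DLT. Taken together, Sections 6.2.1 and 6.3 let that patient stand as one of the three.

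The error runs one way, towards clearing levels that full observation might not have cleared. The RP2D is a primary endpoint (Section 2.7) and sets the dose for up to 32 expansion patients.

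The protocol already accepts the principle. Section 4.5 bars moderate or strong CYP3A inducers in the DLT evaluation period because lower exposure would make the MTD look higher than it is. Other sections make incomplete Cycle 1 exposure foreseeable: stopping at any time (3.12), a lower venetoclax start for patients at particularly high tumor lysis risk (7.4.1.3), venetoclax reduction with azole prophylaxis (7.4.4.1) and delay for infection (7.4.4.2). In addition, one hematologic DLT criterion requires grade 4 toxicity lasting more than 7 days or complicated by hemorrhage. A patient lost before that duration is reached could go unscored.

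**Working it through.** **The plan's own figures.** No operating characteristic is stated for the 3+3, so there is none to reproduce on this point. The only calculated figures, for the expansion cohort's Simon design, do reproduce (type I error 0.0997, power 0.8038, early stopping under the null 72.16%), but they do not bear on dose finding.

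**Inputs.** From the documents: escalation on 0 DLTs in 3, and three more patients after a DLT (6.2.1). Assumed: a true DLT rate p; a share d of patients leaving Cycle 1; and that one DLT in six clears a level. Section 6.2.1 states the last rule for DL-1 and DL-2 but not for DL1 to DL3.

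**Step 1. First cohort only, one of three patients wholly unobserved and scored DLT-free.** The chance of seeing no DLT changes from (1-p)^3 to (1-p)^2.

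- p = 0.33: 0.67^3 = 0.301; 0.67^2 = 0.449.
- p = 0.40: 0.60^3 = 0.216; 0.60^2 = 0.360.

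**Step 2. Clearing a level.** With full observation, P = (1-p)^3 + 3p(1-p)^2 × (1-p)^3. With one unobserved patient in the first three, P = (1-p)^2 + 2p(1-p) × (1-p)^3.

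- p = 0.30: 0.343 + 0.441 × 0.343 = 0.494; with the leaver, 0.490 + 0.420 × 0.343 = 0.634.
- p = 0.40: 0.216 + 0.432 × 0.216 = 0.309; with the leaver, 0.360 + 0.480 × 0.216 = 0.464.

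**Step 3. Averaging over how often patients leave.** Steps 1 and 2 are conditional on a leaver being present. If each patient leaves with probability d and none of a leaver's DLTs is seen, replace p by q = p(1-d) in the full-observation formula. If leavers are observed for half their risk on average, q = p(1-d/2).

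The documents give no Cycle 1 drop-out rate. The 11% and under-15% figures in Section 7.2 are not specific to Cycle 1 and serve here only as an upper range.

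| True DLT rate | Leavers replaced | d = 5% | d = 11% | d = 15% |
|---|---|---|---|---|
| 30%, leavers unobserved | 49.4% | 52.5% | 56.3% | 58.9% |
| 30%, leavers half observed | 49.4% | 51.0% | 52.8% | 54.1% |
| 40%, leavers unobserved | 30.9% | 34.3% | 38.5% | 41.5% |
| 50%, leavers unobserved | 17.2% | 20.2% | 24.1% | 27.0% |

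The chance of at least one leaver among the first three is 1-(1-d)^3: 14.3%, 29.5% and 38.6% at the three values of d.

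**Step 4. Low end.** Spreading 15% evenly over 12 cycles, again an assumption, gives 15%/12 = 1.25% in Cycle 1. Then q = 0.30 × 0.9875 = 0.29625 and P = 50.2%, a rise of 0.8 points.

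**The case against.** A reader might infer that the plan instructs investigators to score early leavers as DLT-free. It does not. Section 6.3 names the population and is silent on scoring. Section 6.2.1 speaks of no DLT within a 28-day cycle, which could be read as needing a completed window. The result described here is the literal consequence of two sections read together, not an express rule.

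The other safeguards have weight:

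- **Replacement.** Section 3.13 refers to the analyses in Section 6, which include the 3+3, so replacing a dose-finding leaver is permitted. But it is optional, and Section 6 supplies no DLT criterion for when to do it.
- **Follow-up.** With 30 days of adverse event follow-up after the last dose, anyone who stops drug in Cycle 1 and stays in follow-up is observed past day 28. Only withdrawn consent or loss to follow-up leaves the window unobserved. This limits the worst case, but off-drug follow-up does not restore exposure.
- **Integrated evaluation and weekly safety review (6.2.1, 10.1).** These make a purely mechanical miscount less likely. Neither says how an incomplete patient is to be counted.

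A reader might also take the rise from 30% to 45% in Step 1 as the general size of the bias. It holds only when one of three patients is wholly unobserved. Nor is it secure that 32 further patients would receive the dose: Section 6.2.2 counts dose-finding patients treated at the RP2D towards expansion accrual, and the first stage can stop at 15. The upward error is also capped by the top dose level in Table 2.

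**Conclusion.** The point holds as a defect in the stated analysis set. All-treated is right for adverse event and discontinuation rates and wrong for dose decisions, and nothing else in the documents supplies the missing definition. The direction is upward.

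The size depends on an unknown Cycle 1 drop-out rate. At a 30% true DLT rate, the average rise in the chance of clearing a level is about 3-10 points at most for an assumed 5-15% drop-out, about half that with partial observation, and under 1 point near 1%. The 14-point rise (49.4% to 63.4%) is the conditional worst case. All clearing probabilities assume that one DLT in six clears. The average effect may be small, but in cohorts of three a single incomplete patient can decide a level, so the rule should be settled in advance.

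**What to change.** In Section 6.3, base escalation and RP2D decisions on a DLT-evaluable set: patients who have a DLT in Cycle 1, whatever their exposure, and patients who complete the 28-day window with a minimum Cycle 1 exposure that the sponsor specifies in advance. In Section 3.13, make replacement of other dose-finding patients mandatory for dose decisions, and have Section 6.2.1 refer to the new set. Keep the all-treated population for adverse event and discontinuation rates, so that no treated patient drops out of the safety tables.

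The cost is about a paragraph of text and possibly one or two replacement patients, which Section 3.13 already permits. Each replacement may delay the next dose decision by up to one 28-day window after that patient starts. No dose level or DLT criterion changes.
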